#### **Secondary Outcome Measures:**

- Change in BPDAI (6) on day 0 to week 12.
- BPDAI on Day 0, Week 2, 4, 6, 8, 10, 12
- Total dose of prednisone required during phases of treatment
  - Treatment Epoch 1 (weeks 0-12)
- Anti-BP180 IgG and anti-BP230 IgG levels by ELISA assay at weeks 0, 4, 8, 12
- Change in neutrophil and eosinophil counts at weeks 0, 4, 8, 12
- Changes in disease activity after discontinuation of Taltz (Ixekezumab)
  - First onset of new blisters
  - BPDAI (week 12 to week 18)
- Clinical safety of Taltz (Ixekezumab) as assessed by vital signs, clinical laboratory variables, and adverse events monitoring

**Exploratory Outcome Measures:** Interleukin (IL)-6, -17, -22, -23, Transforming Growth Factor beta (TGFβ), and matrix-metalloprotease-9 (MMP-9) expression in serum and blister fluid at weeks 0, 4, 8, 12). RNA changes in the blood, blister fluid, and archival tissue biopsy.

For more details on measures rationale see [Supplemental 1: Appropriateness of Measures](#)

### **Safety Measures:**

A thorough baseline screening will be followed for all patients and is outlined in [Table-2](#). A detailed list of the methods in which baseline screening will be performed is outlined in [Supplemental 2](#). All blood draws and safety assessments must be performed **prior** to study treatment administration. Appropriate safety assessments (e.g., evaluation of AEs and SAEs) should be repeated after dosing with study treatment. A physical examination, including general appearance and vital signs, will be performed as indicated in [Table-2](#). If indicated, based on medical history and/or symptoms, additional exams will be performed at the discretion of the investigator. If possible, the same member of the study site staff throughout the study will perform assessments for an individual subject. Information for all physical examinations will be included in the source documentation at the study site. Significant findings that are present prior to the subject signing informed consent will be included in the Medical History. Significant findings made after the signing of the informed consent, which meet the definition of an AE, must be recorded as an AE. Vital signs (blood pressure, pulse, height, weight) will be assessed at each physical examination as indicated in [Table-2](#) (see [Supplemental 2](#) for details on how to acquire vital signs). Whether action needs to be taken to address notable vital signs will be decided by the investigator, taking into account the overall status of the subject. Laboratory studies will be drawn as indicated in [Table-2](#). Whether action needs to be taken to address notable laboratory values will be decided by the investigator, taking into account the overall status of the subject. Hematology assessments will be measured at all scheduled study visits specified in [Table-2](#). Serum chemistry will be a comprehensive metabolic panel will be measured at all scheduled study visits specified in [Table-2](#).

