#### **Investigational and reference therapy:**

*Investigational:* Taltz (ixekizumab) 80mg subcutaneous (160mg week 0, then 80mg weeks 2, 4, 6, 8, 10, & 12)(7)

*Control (prior to washout):* Standard of care therapy prior to washout

*Rescue Therapy:* Prednisone (see [Supplement 4](#))

**Study design:** This is a single center, exploratory, open-label, single-arm design study of 12 patients. Treatment naïve and treatment refractory patients will be treated with Taltz (Ixekizumab). Patients who are non-responders, to physician choice standard of care, will undergo a washout period and will be enrolled in the study. The study consists of 3 epochs: screening/washout period (of at least 1 week and up to 4 weeks), treatment epoch (of 12 weeks from screen/washout), and follow up epoch (of 6 weeks). The screening and washout period will allow for treatment naïve/ new diagnosis BP to undergo evaluation and diagnosis and for treatment refractory to undergo a washout. The total duration of the study will be 18 weeks.

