### **Safety Monitoring:**

The occurrence of adverse events will be sought by non-directive questioning of the patient at each visit during the study. Adverse events also may be detected when the patient volunteers them during or between visits or through physical examination, laboratory test, or other assessments. Please see [Supplemental 3](#) for a detailed description of safety monitoring. Clinically significant abnormal laboratory values or test results will be identified through a review of values outside of normal ranges/clinically notable ranges, significant changes from baseline or the previous visit, or values which are considered to be non-typical in patient with underlying disease. Investigators have the responsibility for managing the safety of individual patient and identifying adverse events. Alert ranges for labs and other test abnormalities are included determined by the Mayo Clinic Arizona and Mayo Medical Laboratory. Adverse events will be recorded in the Adverse Events Case Report Form (CRF) under the signs, symptoms or diagnosis associated with them, and severity. All adverse events will be treated appropriately. Once an adverse event is detected, it should be followed until its resolution or until it is judged to be permanent, and assessment should be made at each visit (or more frequently, if necessary) of any changes in severity, the suspected relationship to the study drug, the interventions required to treat it, and the

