**Table-2: Screening and Visits**

	Screening	Day 0	Week 2	Week 4	Week 6	Week 8	Week 10	Week 12	Week 18
Ixekizumab		X	X	X	X	X	X	X	
Physical Exam	X	X	X	X	X	X	X	X	X
Adverse Event Assessment		X	X	X	X	X	X	X	X
Chest X-ray	X								
BPDAl		X	X	X	X	X	X	X	X
Photographer		X	X	X	X	X	X	X	X
ECG	X								
Venipuncture	X	X		X		X		X	
Serum Pregnancy Test	X								
anti-BMZ autoantibodies	X								
CRP-C reactive protein	X								
anti-BP230 IgG	X	X		X		X		X	
anti-BP180 IgG	X	X		X		X		X	
CMP	X					X			
CBC	X	X		X		X		X	
Quantiferon Gold	X								
Hepatitis B	X								
Hepatitis C	X								
HIV	X								
Coccidioidomycosis	X								
HbA1c	X								
Interleukin 6, 17, 22, 23		X		X		X		X	
TGFb- Transforming growth factor beta		X		X		X		X	
MMP-9 Matrix-metalloprotease-9		X		X		X		X	

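### Serum chemistry is scheduled only at Screening and before the Week 8 dose, so 3 of 7 doses have no later panel and there is no end-of-treatment value

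*Combined protocol and SAP*

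**What the plan says.** - **Outcome.** Secondary Outcome Measures lists the clinical safety of ixekizumab "as assessed by vital signs, clinical laboratory variables, and adverse events monitoring".
- **Chemistry rule.** Under Safety Measures, "Serum chemistry will be a comprehensive metabolic panel will be measured at all scheduled study visits specified in" Table-2. The text sets no visits of its own; the schedule decides.
- **Timing.** The same section states that "All blood draws and safety assessments must be performed" before study treatment is given.
- **Schedule.** In "Table-2: Screening and Visits", the CMP row is marked at Screening and Week 8. The venipuncture and CBC rows are marked at Screening, Day 0 and Weeks 4, 8 and 12. Physical examination, adverse event assessment and BPDAI continue to Week 18.
- **Dosing.** Investigational and reference therapy gives "160mg week 0, then 80mg weeks 2, 4, 6, 8, 10, & 12".
- **Other checks.** Under Safety Monitoring, "The occurrence of adverse events will be sought by non-directive questioning of the patient at each visit during the study". Under Safety Measures, where history or symptoms call for it, "additional exams will be performed at the discretion of the investigator". Supplemental 3 adds a glucose check at each visit for patients given prednisone, and infection checks that use vital signs.

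**The concern.** Haematology is sampled up to the last dosing visit, but chemistry stops four weeks earlier. Supplemental 3 (Abnormal Labs) allows a symptom-free abnormal value to count as an adverse event if it is judged clinically important. That route needs a sample, and none is scheduled for chemistry after Week 8. A silent renal or hepatic change arising late in treatment could therefore go unrecorded, and the laboratory part of the safety outcome would have one on-treatment chemistry value per patient and none at the end of treatment.

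The baseline is also less clean than it could be. Research Design plans a screening/washout period of 1 to 4 weeks, and Table-1 requires drugs such as methotrexate, cyclosporine and azathioprine to be stopped in advance. The plan does not say where in that period the Screening CMP falls. In refractory patients it may precede or overlap washout, so the change from Screening to Week 8 could mix withdrawal of an earlier drug with the effect of ixekizumab.

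A minor related point: the infection check relies on vital signs, but Safety Measures says "Vital signs (blood pressure, pulse, height, weight) will be assessed at each physical examination", a list without temperature.

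**Working it through.** The plan gives no figure to reproduce here; the check is a count of Table-2 cells. A column shift in the extracted table is unlikely, because the CMP row has the full number of fields and both marks fall on venipuncture visits.

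**Inputs**
- Doses: Weeks 0, 2, 4, 6, 8, 10, 12 = 7 (Investigational and reference therapy; Table-2).
- Visits after the first dose: Weeks 2, 4, 6, 8, 10, 12, 18 = 7 (Table-2).
- CMP: Screening, Week 8. CBC: Screening, Day 0, Weeks 4, 8, 12 (Table-2).
- Draws come before the dose (Safety Measures), so a sample covers only doses at earlier visits.
- Planned patients: 12 (Sample Size Computation and Power Analysis).

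**Coverage as written**
- Visits after the first dose with a panel: CMP 1 of 7 (Week 8); CBC 3 of 7 (Weeks 4, 8, 12).
- Doses with no later scheduled CMP: Weeks 8, 10 and 12 = 3/7 = 43%, or 12 × 3 = 36 of 12 × 7 = 84 planned patient-doses. For CBC: Week 12 only = 1/7.
- Treatment time after the last CMP: (12 − 8)/12 = 33%, or 12 × 4 = 48 of 12 × 12 = 144 patient-weeks if all 12 patients complete.
- To the Week 18 visit: (18 − 8)/18 = 56%.

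**Illustration of what a Week 12 panel adds**

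Assume a silent change starts at time t, equally likely anywhere in Weeks 0–12, and lasts L weeks. A sample at week s finds it if t ≤ s ≤ t + L. Week 8 alone finds min(L, 8)/12. With Weeks 8 and 12, the onset times that are caught are the union of the two windows.

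| Duration L | Week 8 only | Weeks 8 and 12 |
|---|---|---|
| 2 weeks | 2/12 = 17% | 4/12 = 33% |
| 4 weeks | 4/12 = 33% | 8/12 = 67% |
| 8 weeks or more | 8/12 = 67% | 12/12 = 100% |

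The shares depend on the onset window. If onset is spread over Weeks 0–18 instead, the figures for L = 2, 4 and 8 are 2/18, 4/18 and 8/18 = 11%, 22% and 44% for Week 8 alone, and 4/18, 8/18 and 12/18 = 22%, 44% and 67% with Week 12 added. For L = 2 and 4 the second sample doubles the share under either window; for L = 8 it raises it by half. These are shares of changes that occur. They do not say how often one occurs, and they ignore unscheduled testing.

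**Coverage after the change**
- CMP at Week 12 added: doses at Weeks 0–10 have a later sample, 6 of 7, as for CBC.
- Week 18 added as well: 7 of 7.

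**The case against.** The strongest reply is that nothing here is inconsistent. The chemistry sentence defers to Table-2, the safety outcome sets no time point for chemistry, and the SAP promises mainly descriptive summaries, so the outcome can be reported as planned. That is right, and it makes this a point about the schedule rather than a contradiction.

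The CBC dates are also no safety standard. Neutrophil and eosinophil counts are a secondary outcome at Weeks 0, 4, 8 and 12, which explains those dates. This stands; the comparison shows only that blood is already being taken.

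The risk is probably low. The documents name no renal or hepatic signal, and entry criteria exclude serum creatinine above 2.0 mg/dL and hepatitis B or C. By the Week 8 panel a patient has received 160 + 3 × 80 = 400 of 160 + 6 × 80 = 640 mg, or 62.5%. An abnormality found then and judged an adverse event is followed to resolution or until judged permanent. All of this lowers the stakes, but none of it supplies a sample after Week 8.

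The other safeguards are partial. Questioning finds what patients notice, discretionary examinations are prompted by history or symptoms, and the glucose check covers only prednisone users. A wholly silent change can pass all three.

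Finally, Screening is a usable baseline, so a Day 0 panel is not essential. That is fair. It is the lesser part of the change, justified by washout and by the draw already being scheduled.

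**Conclusion.** The concern holds. Followed as written, the plan schedules no CMP after 3 of 7 doses, none in the last 4 of 12 treatment weeks, and none at the end of treatment, although laboratory variables are a named safety outcome. The counts rest only on Table-2 and the rule that draws precede dosing. The detection shares rest on an assumed onset distribution and are illustrative.

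The consequence is limited: late, silent chemistry changes may be missed, and chemistry change can be described only from Screening to Week 8. Symptomatic changes have other routes to detection. Efficacy endpoints and the validity of the trial are not affected. The change is worth making because it improves the safety data at very little cost.

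**What to change.** 1. **Main change.** In Table-2, mark the CMP at Week 12, on the existing draw: 12 panels and no new venipuncture.
2. **Cleaner baseline.** Mark the CMP at Day 0, also on an existing draw: 12 more panels, so 2 × 12 = 24 in all.
3. **Analysis.** State that chemistry is summarised as change from Day 0 to Weeks 8 and 12.
4. **Optional.** Add a CMP at the existing Week 18 visit. Without it the Week 12 dose has no later sample. It costs one venipuncture and one panel per patient, 12 of each.
5. **Minor.** Add temperature to the vital signs listed in Safety Measures: one reading at visits that already include a physical examination.

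This takes a short amendment to Table-2 and the related wording.

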### **Safety Monitoring:**

The occurrence of adverse events will be sought by non-directive questioning of the patient at each visit during the study. Adverse events also may be detected when the patient volunteers them during or between visits or through physical examination, laboratory test, or other assessments. Please see [Supplemental 3](#) for a detailed description of safety monitoring. Clinically significant abnormal laboratory values or test results will be identified through a review of values outside of normal ranges/clinically notable ranges, significant changes from baseline or the previous visit, or values which are considered to be non-typical in patient with underlying disease. Investigators have the responsibility for managing the safety of individual patient and identifying adverse events. Alert ranges for labs and other test abnormalities are included determined by the Mayo Clinic Arizona and Mayo Medical Laboratory. Adverse events will be recorded in the Adverse Events Case Report Form (CRF) under the signs, symptoms or diagnosis associated with them, and severity. All adverse events will be treated appropriately. Once an adverse event is detected, it should be followed until its resolution or until it is judged to be permanent, and assessment should be made at each visit (or more frequently, if necessary) of any changes in severity, the suspected relationship to the study drug, the interventions required to treat it, and the

outcome (see [Supplemental 3](#)). Information about common side effects already known about the investigational drug can be found in the package insert. This information will be included in the patient informed consent and should be discussed with the patient during the study as needed. The investigator will also instruct each patient to report any new adverse event (beyond the protocol observation period) that the patient, or the patient's personal physician, believes might reasonably be related to study treatment. This information should be recorded in the investigator's source documents, however, if the AE meets the criteria of an SAE. To ensure patient safety, every SAE (see [Supplemental 3](#) for definition), regardless of suspected causality, occurring after the patient has provided informed consent and after the patient begins taking study drug and until 30 days after the patient has stopped study participation will be recorded and reported to Lilly. Any SAEs experienced after this 30-day period should only be reported to Lilly if the investigator suspects a causal relationship to the study drug. All malignant neoplasms will be assessed as serious under "medically significant" if other seriousness criteria are not met. Medical and scientific judgment will be exercised in deciding whether other situations should be considered serious reactions, such as important medical events that might not be immediately life threatening or result in death or hospitalization but might jeopardize the patient or might require intervention to prevent one of the outcomes listed in SAE. Any suspected transmission via a medicinal product of an infectious agent is also considered a serious adverse reaction. All AEs (serious and non-serious) are captured and recorded, SAEs also require individual reporting (see [Supplemental 3](#)). To ensure patient safety, each pregnancy occurring while the patient is on study treatment must be reported to the sponsor-investigator within 24 hours of learning of its occurrence. The pregnancy should be followed up to determine outcome, including spontaneous or voluntary termination, details of the birth, and the presence or absence of any birth defects, congenital abnormalities, or maternal and/or newborn complications. Pregnancy follow-up should be recorded on the same form and should include an assessment of the possible relationship to the study treatment. Any SAE experienced during the pregnancy and unrelated to the pregnancy must be reported on a SAE form.

#### **Sample Size Computation and Power Analysis:**

The sample size for this pilot study is set at 12 patients for logistical and financial reasons. This is similar in size to other exploratory studies and will provide adequate data for estimation purposes for planning future studies. With 12 patients, the study is intended to be for estimation purposes only.

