### **Research Design:**

This is a single center, exploratory, open-label, single-arm design study of 12 patients with BP. Treatment naïve and treatment refractory patients with BP will be treated with Taltz (Ixekizumab). Patients who are non-responders, to physician choice standard of care, will undergo a washout period and will be enrolled in the study. The washout period is 2 weeks for systemic non-immunosuppressive agents, topical steroids, and topical calcineurin inhibitors. A 4-week washout period will be used for systemic systemic immunosuppressive agents or 5 half-lives, whichever is longer, and no live vaccines should be administered within 12 weeks of the study drug. ([Table-1](#)) The study consists of 3 epochs: screening/washout period (of at least 1 week and up to 4 weeks), treatment epoch (of 12 weeks from screen/washout), and follow up epoch (of 6 weeks). The screening and washout period will allow for treatment naïve/ new diagnosis BP to undergo evaluation and diagnosis and for treatment refractory to undergo a washout. The total duration of the study will be 18 weeks.

The duration of treatment, 12 weeks, is based upon the maximal efficacy and dosing regimen of Taltz (Ixekizumab) in psoriasis.(7) Although psoriasis and BP are different disease processes, we would expect a response by 12 weeks of treatment. The open-label, single-arm design will allow for the assessment of the effects of Taltz (Ixekizumab) monotherapy in patients with acute and chronic disease in a relatively short time frame and will minimize study costs. This is critical as there may be a significant benefit either earlier or later in the disease course. This design will also allow for more patients to undergo targeted, serological analysis, which will provide in-vivo evidence of the pathogenesis of disease as well as the changes that occur during treatment. The open-label design of this study will have assessment bias on the part of the patient as well as the physician. The single-arm design will not allow for blinded assessment. In order to mitigate these issues, we will be using objective and validated methods of clinical assessment, which should be robust including: new blister formation, BPDAI, and prednisone usage. Additionally, the serological markers, which are secondary endpoints, will be assessed as an unbiased corollary to the primary effects of Taltz (Ixekizumab) on BP patients.

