#### **Statistical Analysis Plan:**

**Design:** This is an exploratory single center, open-label design study in approximately 12 patients. Safety of Taltz (Ixekizumab) in the treatment of the autoimmune blistering disease, BP will be evaluated. Changes in new blister formation will also be explored.

**Primary Endpoint:** The primary endpoint will be median time from first dose of Taltz (Ixekizumab) treatment to cessation of any new blisters.

**Secondary Endpoint(s):** The secondary endpoints will include change in BPDAI from day 0 to week 12, total dose of prednisone required during the therapeutic time period at weeks 0-12. Additional analysis will be performed on serological markers, disease activity after drug discontinuation, and safety monitoring. Descriptive statistics and graphical plots will be mainly used to summarize the data and estimate primary and secondary endpoints.

**Primary Analysis:** Calculation of the time from first dose of treatment until cessation of any new blisters will be conducted and summarized using means, standard deviations and 95% confidence intervals. Blister formation will be summarized at baseline and subsequent time points (using means, standard deviations and 95% confidence intervals). Change in blister formation (any new blisters) from baseline will be calculated by subtracting the baseline number of blisters from the number of blisters at each evaluation. Graphical displays will be produced; such as mean profile plots or bar charts.

**Secondary Analyses:** Analyses for secondary endpoints will also be descriptive in nature. Adjustment for multiple comparisons for the secondary analyses will not be done due to the exploratory nature of this research. Calculation of the change in BPDAI score from baseline to week 12 will be conducted and summarized using means, standard deviations and 95% confidence intervals. Graphical displays will be produced; such as mean profile plots or bar charts.

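### Twelve patients are called adequate for estimation with no precision stated, and the primary median or its upper confidence limit may not be reached; add the week-12 cessation proportion with an exact interval

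*Combined protocol and SAP*

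**What the plan says.** The section Sample Size Computation and Power Analysis gives the practical reason first: "The sample size for this pilot study is set at 12 patients for logistical and financial reasons". It adds that the size resembles that of other exploratory studies and that it "will provide adequate data for estimation purposes for planning future studies". It closes with the limit on its ambition: "With 12 patients, the study is intended to be for estimation purposes only". No expected interval width, SD, cessation rate or dropout rate follows.

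The Statistical Analysis Plan defines the target: "The primary endpoint will be median time from first dose of Taltz (Ixekizumab) treatment to cessation of any new blisters". Under Primary Analysis, however, the times are to be "summarized using means, standard deviations and 95% confidence intervals". No interval for the median is planned, and there is no rule for a patient who is still forming blisters when observation ends.

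On how many patients will respond, Research Design says only that "we would expect a response by 12 weeks of treatment". Treatment lasts 12 weeks and follow-up 6 weeks. Table-2 schedules examination and photography through week 18.

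**The concern.** A study limited to estimation is judged by the precision of its estimates, so the expected precision is the figure this section most needs. *Adequate* stands there instead.

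The primary quantity also makes adequacy depend on the outcome. A median time exists only if about half the patients reach the event, and its upper confidence limit exists only if most of them do. A mean and SD of the times need a time for every patient, and a patient who never stops blistering has none. If a fair share of the 12 do not stop, whoever plans the next study could receive a median with an open upper end, no median at all, or a mean computed on responders only. The plan names no fallback quantity that could still be reported.

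**Working it through.** **Inputs**

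- n = 12: Sample Size Computation and Power Analysis.
- Median as primary endpoint and 95% as confidence level: Statistical Analysis Plan.
- Observation to week 12 on treatment and week 18 in total: Research Design, Table-2.
- True probability p of cessation by week 12: not in the documents. Assumed range 0.4 to 0.9.
- Dropout: not in the documents. Taken as nil below; dropout before cessation would make a finite upper limit less likely.

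The 12 comes from no formula, so there is no figure of the plan's own to reproduce.

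**Step 1: events needed for an upper limit on the median.** The interval from the r-th to the (13−r)-th ordered time has coverage 1 − 2·P(Bin(12, 0.5) ≤ r−1).

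- r = 3: 1 − 2(1+12+66)/4096 = 96.1%.
- r = 4: 1 − 2(1+12+66+220)/4096 = 85.4%, which is too low.

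So the 95% interval runs from the 3rd to the 10th time. With non-responders censored, the 10th time is observed only if at least 10 of 12 patients cease. Kaplan-Meier intervals for the median need 9 (linear), 10 (log-log) or 12 (log). The median itself needs 6, or 7 under a stricter convention.

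**Step 2: chance of enough events**, with X ~ Bin(12, p).

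| Assumed p | Median reached, P(X ≥ 6) | Finite upper limit, P(X ≥ 10) |
|---|---|---|
| 0.4 | 33% | under 1% |
| 0.5 | 61% | 2% |
| 0.6 | 84% | 8% |
| 0.7 | 96% | 25% |
| 0.8 | over 99% | 56% |
| 0.9 | over 99% | 89% |

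Example at p = 0.8: 66·0.8¹⁰·0.2² + 12·0.8¹¹·0.2 + 0.8¹² = 0.283 + 0.206 + 0.069 = 0.558.

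Solving P(X ≥ k) = 0.5 for p gives the break-even rate: 0.78 for k = 10, 0.70 for k = 9, and 0.5^(1/12) = 0.94 for k = 12.

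**Step 3: effect of counting week 18.** Assume exponential times with a true median of 6 weeks. Then p is 1 − 0.5^(12/6) = 0.75 by week 12 and 1 − 0.5^(18/6) = 0.875 by week 18. The chance of at least 10 cessations rises from 39% to 82%.

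**Step 4: the planned mean and SD**, supposing all 12 times are observed and roughly normal.

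- The 95% half-width for the mean is t(0.975, 11)/√12 = 0.64 SD.
- The 95% limits for true variance over estimated variance are 11/χ² on 11 df, 0.50 to 2.88. The true SD is therefore 0.71 to 1.70 times the estimate.
- A later sample size is proportional to the variance. The size computed from the pilot SD, divided by the right size, is the reciprocal: 1/2.88 = 0.35 to 1/0.502 = 1.99.

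**Step 5: an alternative that needs no reached median.** The exact 95% interval for the proportion with cessation by week 12 is 21 to 79% for 6/12 and 35 to 90% for 8/12.

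**The case against.** The plan is open that 12 is a practical number for a pilot and resembles other exploratory studies. Research Design separately defends the single-arm layout on time, cost and serological yield. That stands. A reader might infer that 12 is the wrong number, or that adequacy for estimation is its only justification. The documents support neither. Adequacy is only the one statistical reason among several.

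No document gives a cessation rate, and the one stated expectation, a response by week 12, is optimistic. A reader might infer that the upper limit will usually be missing. That holds only below a true rate of about 78% with the exact interval; at 90% the limit would be finite in 89% of such studies.

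The primary endpoint carries no explicit week-12 cut-off, and Step 3 shows that counting week 18 helps considerably. Nor does the plan promise an interval for the median. Both points are fair, but a median reported without an interval gives a planner less, and the mean that the plan does promise fails for non-responders at either horizon.

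The proposed proportion has a wide interval too: 58 percentage points at 6/12. That is true. Its merit is that it can be computed whatever the outcome, once dropouts are assigned.

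Finally, a reader might infer from Step 4 that the SD is useless for sizing a trial. It is imprecise, but it can be used with an allowance.

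**Conclusion.** The point holds in a conditional form. The claim of adequacy rests on no stated precision, and the primary median, or its upper limit, may not be estimable from 12 patients. Under week-12 censoring a finite upper limit needs at least 10 of 12 cessations (9 to 12 by method). The chance of that runs from 2% to 89% as the assumed true rate goes from 50% to 90%. The chance that the median is reached is 33, 61 and 84% at 40, 50 and 60%.

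The result rests on the assumed cessation rates, on the absence of dropout and on week 12 as the horizon; a week-18 horizon is kinder. The SD range needs only n = 12 and approximate normality. The sample size itself is not an error.

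**What to change.** Keep n = 12.

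In the Statistical Analysis Plan, add a planning estimate alongside the median, for example:

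> The proportion of all treated patients whose new blister formation has ceased by week 12 will be reported with an exact 95% confidence interval. Patients who leave the study before cessation count as not ceased.

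In Sample Size Computation and Power Analysis, make the adequacy claim conditional by quoting the expected precision: 21 to 79% if 6 of 12 cease, 35 to 90% if 8 of 12 do. Add that an upper limit for the median will be available only if about 10 or more cease. If the SD is mentioned, state that the true value lies within 0.71 to 1.70 times the estimate (95% limits), so a trial sized on the pilot SD alone would be about 0.35 to 1.99 times the right size. This protocol need not prescribe how a later trial allows for that.

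The cost is one extra summary and a less favourable precision statement. No patient, visit or measurement is added. The proportion does not make the planned mean and SD meaningful for patients without a cessation time; those summaries still need a rule of their own.
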